1.2 ATTR-CM Population Burden

1.2.1 ATTR amyloid is an under-recognized cause of heart failure

Cardiac involvement in ATTR, also known as familial amyloid cardiomyopathy (FAC) when associated with variant and WT TTR aggregation, previously senile systemic amyloidosis (SSA) when associated solely with WT TTR aggregation, is caused by amyloid fibril infiltration of the myocardium. This results in diastolic dysfunction progressing to restrictive cardiomyopathy and HF. ATTR cardiomyopathy is a late onset disease with symptoms typically occurring in patients over 60 years old. Although there are more than 20 mutations which have been associated with specific cardiac involvement, one mutation, Val122Ile, has been reported with high frequency in Blacks (prevalence of 3.4% to 3.9%^{5, 45, 46}). The prevalence of ATTR dominated by a cardiomyopathy phenotype is unknown, but is certainly under-diagnosed⁴³. Both Black Val122Ile carriers and Black patients with ATTRwt, who present typically after age 60, are often mistakenly thought to have hypertensive heart disease⁴³. The prevalence of the Val122Ile allele in older adults with manifest cardiovascular disease, such as HF, is much higher. Among 207 of 650 Blacks enrolled in the BEST Trial with NYHA Class III (92%) and IV (8%) HF, with a left ventricular ejection fraction <35%, the Val122Ile variant was found in 13 (6.3 %) of the subjects⁴⁷. Of note, four of the 116 individuals in the under 60 years of age cohort (3.5%) were positive, whereas 9 of the 91 over 60 years of age (10%) had the amyloidogenic Val122Ile allele. Studies indicate that the Val122Ile mutation is 5 times more prevalent in Blacks with HF than in a community cohort of comparable age⁴⁷. Notably, a mutation in TTR is not a prerequisite for developing ATTR cardiomyopathy. In the elderly, WT (normal) TTR may become structurally unstable for unknown reasons (this will be quantitatively explored herein), resulting in deposition of amyloid fibrils primarily in heart tissue and leading to HFpEF⁴⁸⁻⁵¹. The frequency of TTR amyloid deposition in cardiac ventricles reported from autopsy studies, range from 1.8% to 25%^{52, 53}, with a rate of clinical cardiac disease pre-mortem of 34%⁵². More recent data demonstrates that among HFpEF subjects who were an average age of 74±14 at diagnosis, 21.2% had amyloid deposits on autopsy performed at an average age of 76±14 years. Of HFpEF patients ≥ age 75 years at HF diagnosis (n = 63), 20 (32%) had amyloid deposition vs. 4 of 50 (8%) patients < 75 years at HF diagnosis (p = 0.002). Of the 29 patients with amyloid deposition at autopsy, only 6 had a pre-morbid diagnosis of amyloid

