2.1.3 Patient Recruitment

The SCAN- MP study is designed to identify a sufficient number of cases to support the following analytical objectives:

1. Stratify prevalence of ATTR-CA in subjects with HF by relevant demographic characteristics (gender, race/ethnicity, genotype); and
2. Evaluate relationships among ATTR-CA and baseline risk factors (presence of Val122Ile mutation and others) with disease outcomes.

To accomplish these objectives, a hybrid approach to cohort identification and selection is used that combines deliberate selection of subjects with heart failure who are at increased risk for ATTR-CA and selection of participants with relevant characteristics (age, gender, race/ethnicity, country of origin). Planned proportion of enrolled subjects by relevant characteristics is shown in the Table 3. Community involvement is essential for its success and recruitment will involve intensive community engagement through various means among the sites. In aggregate, we will recruit an equal number of men and women from the racial/ethnic groups. The expected marginal distributions of race/ethnicity are shown in Table 3. We will have overlapping ethnic groups among centers to minimize confounding of ethnicity by site. As recruitment of elderly members of minority groups is challenging, toward end of the recruitment period, participants will be asked to refer elderly persons to the study.

Table 3. Planned Enrollment by Age, Race, and Gender

Age (yr)	Black		Hispanic or Latino ethnicity		Total	
	M	F	M	F	M	F
≤75	150	150	50	50	200	200
>75	150	150	50	50	200	200

At CUMC we have seen 24,682 unique patients with HF over the last five years of which 2,969 (12%) self-identified as Black and 4,387 of 14,466 (29.9%) patients who declared their ethnicity were Hispanic and whose average age was 63 years. Harlem Hospital provides health care services to the primary service area of Harlem, Washington Heights/Inwood and the South Bronx with the vast

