2.1.8 Data Analysis Plan

Descriptive statistics will be used to summarize subjects' demographics and study outcomes. Sample proportions with exact 95% confidence intervals will be used to estimate the overall prevalence of ATTRm CA in Blacks and Hispanics and by sex. All analyses will be performed in SAS v.9.4 (Cary,NC), at a significance level of 0.05.

AIM 1: Hypotheses 1-3: The differences in proportions for prevalence (#1), genetic mutation status (#2), and sex (#3) will be assessed using Chi-squared/Fisher Exact tests. The genetic ancestry analysis will use 500K SNP data to perform principal components analysis (PCA) and determine the percentage of African admixture in all participants. To identify the associations of rare genetic variants in the TTR gene in ATTR CA cases vs controls, we will utilize burden testing.⁹⁴ **Hypothesis 4:** The main analysis will use the Kaplan-Meier method to estimate the probabilities of the composite endpoint, with medians (95% CI) being reported for each group. Cox regression analysis will be performed to generate the hazard ratio (95% CI), and to allow adjustment for other covariates such as sex or race/ethnicity, or explore interaction with other variables including cardiac biomarkers, echo parameters, or QOL. Alternatively, we will apply and compare Finkelstein-Schoenfeld's unmatched approach⁹⁵ to the matched win ratio,⁹⁶ both methods being used for reporting composite endpoints, with more appropriate priority given to the more clinically important event, e.g. mortality. **Hypothesis 5:** We will test the clinic-based risk calculator that was previously developed and validated in a smaller matched cohort study.⁹⁷ The proposed 4-variable model included: RBP4, LVEF, inter-ventricular septal thickness, mean limb lead QRS voltage, and generated an ROC AUC >90%. This model will be tested in our larger cohort and assessed with respect to prediction capability (AUC ROC) and goodness-of fit (Hosmer-Lemeshow test). We also plan to fit additional multivariable logistic regressions using the variables collected employing variable selection/model-building strategies and comparing the

resulting model(s) to the one proposed above. The variables in the final clinical risk model will be based on weights from the multivariate model.

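### Aim 1 prevalence is a crude proportion from a sample planned to be half over age 75, with no age-specific or standardised estimate

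*Combined protocol and SAP*

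**What the plan says.** Specific Aim 1 (section 2.1.1) is to determine how common ATTR cardiac amyloidosis is among Black and Caribbean Hispanic patients with heart failure; the hypothesised figure is 10-15%.

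Section 2.1.3 describes a purposive sample. The approach "combines deliberate selection of subjects with heart failure who are at increased risk for ATTR-CA and selection of participants with relevant characteristics". "Planned proportion of enrolled subjects by relevant characteristics is shown in the Table 3", and the table is headed "Table 3. Planned Enrollment by Age, Race, and Gender". It gives 150 Black and 50 Hispanic participants in each of four age-by-sex cells. The text adds "In aggregate, we will recruit an equal number of men and women from the racial/ethnic groups" and, because older members of minority groups are hard to recruit, "toward end of the recruitment period, participants will be asked to refer elderly persons to the study".

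Section 2.1.6 (Aim 1, Hypothesis 1) defines prevalence as wild-type plus mutant cases as a percentage of everyone enrolled. Section 2.1.8 states: "Sample proportions with exact 95% confidence intervals will be used to estimate the overall prevalence of ATTRm CA", in Blacks and Hispanics and by sex. That sentence is worded for ATTRm only. The strata listed in section 2.1.3 for prevalence are gender, race/ethnicity and genotype. Nowhere is there a weight, an age-specific prevalence, a standardised prevalence or a description of the age mix of eligible patients. Covariate adjustment is planned for the progression model (Hypothesis 4), not for prevalence.

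**The concern.** A sample proportion estimates population prevalence only if the sample has the population's mix on whatever drives prevalence, or is weighted back to it. Here the age mix is chosen by design, and the protocol itself treats age as a strong driver. Section 1.2.1 cites an autopsy series in heart failure with preserved ejection fraction, where, of those aged 75 or more at diagnosis, "20 (32%) had amyloid deposition vs. 4 of 50 (8%) patients < 75 years at HF diagnosis".

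If older patients are over-represented, the headline prevalence is too high. So is every by-race and by-sex figure, since each carries the same planned half aged over 75. The planned outputs would not let a reader undo this, because no age-specific figures are promised. The exact confidence interval reflects sampling error only. At stake is the absolute Aim 1 prevalence and its comparison with 10-15%.

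**Working it through.** **1. Reproduce the plan's figures.** Table 3: 4 × 150 + 4 × 50 = 800, of whom 600 are Black and 200 Hispanic, matching section 2.1.7. Aged over 75: 400/800 = 50%. Women: 400/800 = 50%. Autopsy series: 20/63 = 31.7% and 4/50 = 8.0%, a ratio of about 4:1; (20 + 4)/(63 + 50) = 21.2%, as section 1.2.1 reports.

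**2. Formula.** Let *w* be the share of eligible patients aged over 75, *p* the prevalence at 75 or under, and *r* the ratio of prevalence over 75 to prevalence at 75 or under.

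- Crude, at the planned 50:50 mix: C = p(1 + r)/2
- Standardised: S = p[1 + (r − 1)w]
- Overstatement: C/S = (1 + r) / (2[1 + (r − 1)w])

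**3. Inputs not in the documents.** The share *w* is not given. The only age figure for a source population is in section 2.1.3, for the lead site: "patients who declared their ethnicity were Hispanic and whose average age was 63 years". There is no SD. Assuming normal ages with mean 63 and SD 10, 12 or 15, truncated at 60, gives *w* = 0.19, 0.27 or 0.37. I use 0.20, 0.25 and 0.35 as an assumed range.

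**4. Autopsy rates used directly.** At 32% and 8%, the Table 3 mix gives 0.5 × 32 + 0.5 × 8 = 20.0%. For *w* = 0.20, 0.25 and 0.35 the result is 12.8%, 14.0% and 16.4%.

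**5. Scaled to a crude 12.5%** (100/800, the middle of 10-15%; exact 95% CI 10.3-15.0%):

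| Age gradient | w = 0.20 | w = 0.25 | w = 0.35 | Crude ÷ standardised |
|---|---|---|---|---|
| 4:1 for all cases (5% and 20%) | 8.0% | 8.75% | 10.25% | 1.56, 1.43, 1.22 |
| 2:1 for all cases (8.33% and 16.67%) | 10.0% | 10.4% | 11.25% | 1.25, 1.20, 1.11 |
| ATTRm flat at 8%; ATTRwt 4.5% at 4:1 (1.8% and 7.2%) | 10.9% | 11.15% | 11.7% | 1.15, 1.12, 1.07 |
| None | 12.5% | 12.5% | 12.5% | 1.00 |

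In the third row, 8% is the ATTRm figure hypothesised in section 2.1.6 and 4.5% is the remainder. At *w* = 0.20: 8 + 0.8 × 1.8 + 0.2 × 7.2 = 10.88%.

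**6. Against the crude interval.** The exact lower limit for 100/800 is 10.29%. The standardised value is below it in all three 4:1 cases, in one of three 2:1 cases (*w* = 0.20), and in none of the flat-ATTRm cases.

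**7. Sex.** If prevalence were 3:1 male to female and men were 40-60% of eligible patients (both assumed), a crude 15% would standardise to 13.5-16.5%. The direction is unknown, and sex-specific proportions are already planned, so this part is smaller.

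**The case against.** Several stronger readings are tempting and are not supported.

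- **Hard quotas.** A reader might infer that enrolment is capped by cell. Table 3 is described as planned and expected, with no cap or closing rule. This stands, but whatever mix is achieved still goes into the estimate unweighted.
- **4:1 as the gradient for this trial.** The autopsy figures are amyloid deposition by age at heart failure diagnosis, in preserved ejection fraction only, not scan-positive ATTR-CA. The younger group may include patients under 60, whom this trial excludes. Section 2.1.6 expects mostly ATTRm in Black patients, who are 75% of planned enrolment, and ATTRm presents younger (69.5 against 77.2 years at diagnosis, Table 1). With ATTRm flat across ages 60 and over, the overstatement falls to 1.07-1.15 times, inside the crude interval. This stands. Flat ATTRm is the favourable extreme.
- **Known source age.** The mean of 63 years comes from one site, may describe only Hispanic patients, and is not restricted to the entry criteria. In the autopsy series 63/113 = 56% were aged 75 or more at diagnosis. If more than half of eligible patients were over 75, the bias would reverse. So direction as well as size is conditional.
- **Black-Hispanic contrast.** Table 3 balances it on age and sex, so it is not the concern.
- **Hypothesis 3.** A reader might infer that equal recruitment distorts the male share of cases. With equal enrolment that share is p(men)/[p(men) + p(women)], a direct function of the prevalence ratio. It misleads only if the achieved mix departs from 50:50: at 3:1, the share is 67% or 82% with 40% or 60% men, against 75%.

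Weighting by age and sex also cannot repair the deliberate selection of patients at increased ATTR-CA risk. That limits what the fix achieves, but is a further reason not to read the crude figure as a population prevalence.

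**Conclusion.** The concern holds for absolute prevalence, mainly through age. The plan sets the age mix by design, estimates prevalence without weights, and has no step linking the result to the population named in Aim 1. The crude figure overstates prevalence, overall and within each race and sex group, provided that prevalence rises with age and that fewer than half of eligible patients are over 75. Both conditions are plausible, and neither is established by the documents for this population. For an assumed 20-35% over 75, the factor runs from 1.07 (flat ATTRm, 4:1 for ATTRwt) to 1.56 (4:1 for all cases). It would be wrong to say that the true value necessarily falls outside the planned interval; that depends on the gradient. What can be said is that the interval makes no allowance for this error.

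**What to change.** In section 2.1.8:

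1. Report ATTR-CA, ATTRm and ATTRwt prevalence by age band (75 or under, over 75) within sex and race/ethnicity.
2. Beside the crude figure, add a prespecified prevalence directly standardised to the age-sex-ethnicity mix of Black and Hispanic heart failure patients aged 60 or over at the sites. Restrict that reference mix to the entry criteria as far as records allow, and give a stratified confidence interval.
3. If no such reference mix can be obtained, describe the crude figure as prevalence in the enrolled cohort only.
4. State that standardisation does not correct the deliberate selection of patients at increased ATTR-CA risk.
5. For Hypothesis 3, report the male:female prevalence ratio if the achieved sex mix departs from 50:50.

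Cost: wording, plus one aggregate count by age band, sex and ethnicity from site records. Section 2.1.3 shows that the lead site and Boston have already counted heart failure patients, but it gives no age-by-sex breakdown and no heart failure count specific to Harlem or Yale. No new patients, visits or tests are needed. The headline figure will probably be lower and its relative precision somewhat worse. For example, with 6% and 24% in the two age bands and *w* = 0.20 treated as known, the standardised estimate is 9.6% (approximate 95% CI 7.6-11.6%), against a crude 15.0% (exact 12.6-17.7%). The half-width is then about 21% of the estimate (2.04/9.6) instead of about 17% (2.53/15.0).

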2.1.4 Selection Criteria

800 patients will be enrolled in this protocol. **Inclusion Criteria** will include: Black or Hispanic of Caribbean origin, Age \geq 60 years with heart failure and able to understand and sign the informed consent document after the nature of the study has been fully explained, prior to any study procedures. **Exclusion Criteria** will include confirmed primary amyloidosis (AL) or secondary amyloidosis (AA), prior liver or heart transplantation and active malignancy or non-amyloid disease with expected survival of less than 1 year, or heart failure attributable to ischemic or valvular heart disease.

2.1.5 Study Procedures

The timing of all procedures in this study is outlined in Table 4. Eligible patients will be identified. Patients who are interested in the study will have a screening visit to evaluate for eligibility and obtain informed consent. If patients qualify for study and do consent they will have their study visit within 4 weeks of screening. At that visit they will have all of the following testing done.

Table 4. Study Procedures

Procedure	Screening	Baseline	6 Months* (± 2 weeks)	12 Months* (± 4 weeks)
Informed Consent	X			
Inclusion and Exclusion Criteria	X			
Baseline History		X		
Height and weight [†]		X	X	X
Vitals Signs		X	X	X
Medications		X	X	X
Clinical Examination		X	X	X
Adverse Events Review		X	X	X
Electrocardiogram		X	X	X
Laboratory Analysis				
Basic Metabolic Panel		X	X	X
Hepatic Function Panel		X	X	X
Cardiac Biomarkers [‡]		X	X	X
Vitamin A/RBP4 in plasma/urine [§]		X	X	X

Prealbumin		X	X	X
TTR Kinetic Stability		X		X
TTR Gene Sequencing		X		
Ancestry Analysis		X		
Six-Minute Walk Test		X	X	X
Short Physical Performance Battery		X	X	X
QoL Questionnaires		X	X	X
Health Literacy Questionnaire		X		
Echocardiogram		X		X
^{99m} Tc-PYP Scintigraphy**		X		
Phone call follow-up [†]			X	X

* Follow-up visits are to be conducted on subjects who test positive to the cardiac amyloid nuclear scan and/or are carrier of the V122I mutation. Window for the 6-month visit is ± 2 weeks and for the 12-month visit is ± 4 weeks.

[†] Height measured only at baseline visit.

[‡] Includes BNP, NT-proBNP, galectin-3, troponin I and T.

[§] Includes Vitamin A and RBP4 in on site spot urine.

**In the event that PYP is unavailable due to supply shortage, the investigator has the option of using HDP until PYP becomes available again to ensure study continuation per FDA.

¶ For participants with no TTR CA, a phone call follow-up will be conducted instead.

2.1.5.1 Clinical Examination

A detailed⁸² health investigation will be performed in all patients by a provider experienced in the care of patients with HF. This will include a medical history focused on the presence of HF as defined by standard clinical criteria (NHANES⁸³ and European Society of Cardiology⁵⁸ for HFpEF), etiology of HF, NYHA functional class assessed by standardized questionnaires⁸² and co-morbid conditions; physical examination including vital signs both supine and upright, volume status, cardiopulmonary examinations and neurologic examination with focus on neuropathic findings. Exams will take ~ 45 minutes.

2.1.5.2 ^{99m}Tc-PYP Scintigraphy

A nuclear medicine technologist will perform planar cardiac imaging of the chest using dual-headed gamma cameras equipped with low energy, high resolution collimators. 10-25 mCi of ^{99m}Tc-PYP or will be administered intravenously and imaging will be performed after approximately 3 hours. The anterior and lateral planar views centered on the heart will be obtained simultaneously for a total of at least 750K counts/view (approx. 3-8 min of imaging). Cardiac retention will be assessed by both a semi-quantitative visual score (range: 0 [no uptake] to 3 [uptake greater than rib]) and a quantitative heart-to-contralateral (H/CL) ratio of total counts in a region of interest (ROI) over the heart divided by background counts in an identical size ROI over the contralateral chest including soft tissue, ribs, and blood pool. A visual score 2 or greater and/or calculated H/CL ratio 1.3 or greater, with myocardial retention of ^{99m}Tc-PYP confirmed in all cases by SPECT imaging with or without CT attenuation, will

be required to indicate TTR-CA according to prior published data.⁷⁰ The details of the imaging procedures for ^{99m}Tc-PYP or ^{99m}Tc-PYP imaging are shown in Tables 5a-5c below.

Table 5a

Acquisition Procedure - Planar Imaging	
System	Standard Gamma Camera
Participant Position	Supine on the imaging table - raise arms above the head
Collimator	LEHR
Matrix	256 x 256
Peak	140 KeV
Energy Window	15% to 20%
Zoom	1.46 (or closest)
Views	Anterior and Left Lateral
Acquisition Counts	Minimum 750,000 counts

Table 5b

Acquisition Procedure - SPECT Imaging	
System	Standard Gamma Camera
Participant Position	Supine on the imaging table - raise arms above the head
Orientation	Feet First
Organ	Cardiac
Collimator	LEHR
Matrix	64 x 64
Number of Angles	64
Peak	140 KeV
Energy Window	15% to 20%
Zoom	1.46 (or closest)
Acquisition Bit Depth	8 bit or 16 bit
Detector Configuration	90 degree (Cardiac)
Orbit Type	Non-circular or Circular
Orbit Acq	180 degrees
Start Position	0 degrees
Orbit Direction	Counter-Clockwise
Acquisition Type	Step and Shoot
Rotations	1
Time per Stop	30 sec
Total Time	~15 min

Table 5c

Imaging Protocol for CT Attenuation Correction (performed as available)	
Indication: CT attenuation correction	
Breathing Instructions:	Free breathing
Other Instructions:	raised arms above head

Duration:	3 mins
This imaging protocol utilizes a patient's radiation exposure that is as low as reasonable achievable while maintaining diagnostic image quality. Dose modulation software, when utilized, sets an appropriate exposure and CTDI proportional to the patient's size.	
PATIENT POSITION	Supine
SERIES DESCRIPTION	
SCOUT / TOPOGRAM	Standard
AXIAL, HELICAL OR VOLUME	Helical
Tube Potential	120 kV
Tube current (If NO mA modulation)	31 mA
SFOV (mm)	600/500
DFOV (mm)	600/500
DETECTOR COVERAGE (mm)	160x1.5
PITCH-SPEED	0.938
ROTATION TIME (s)	0.75
DOSE MODULATION	N/A
NOISE INDEX	N/A
Scan Length (mm)	216
DLP (mGy.cm)	46.299
CTDI PHANTOM (cm)	32
CTDI _{Ivol} (mGy) (If NO mA modulation)	N/A
DOSE NOTIFICATION VALUE (mGy)	N/A
SCAN ACQUISITION DIRECTION	N/A
NUMBER OF PASSES	N/A
RECON 1	Filtered Back projection
SLICE THICKNESS (mm)	3
INTERVALS (mm)	3
ALGORITHM / KERNEL	B
ITERATIVE RECONSTRUCTION	N/A
SEND TO PACS	Yes

Each Tc-PYP or Tc-HMDP scan will be read by 3 independent readers blinded to clinical information. Previous unpublished data shows a high degree of agreement among four independent readers using a semi-quantitative score (0 to 3) with kappa ranging from 0.882 to 1.00 with an average of 0.95 for 50 scans read independently. When scores were dichotomized by positive (semi-quantitative score of 2 or 3) compared with negative (semi-quantitative score of 0 or 1), the degree of agreement among the readers was even higher (kappa of 0.891 to 1.00). (See Table 6 below) Using the quantitative score system of H/Cl ratio provided greater certainty in characterizing positive and negative scans.

Table 6. Degree of Agreement – DPD Scans Qualitative 0-1 vs 2-3

Group	Kappa	P value
Reader 1 vs. Reader 2	0.947	<0.0001
Reader 1 vs. Reader 3	0.947	<0.0001
Reader 1 vs. Reader 4	0.947	<0.0001

Reader 2 vs. Reader 3	0.891	<0.0001
Reader 2 vs. Reader 4	1.000.	<0.0001
Reader 3 vs. Reader 4	0.891	<0.0001

Based on an international multicenter collaboration, three ^{99}m technetium-labeled radiotracers, ^{99}mTc - ^{99}m -3,3-diphosphono-1,2-propanodicarboxylic acid (DPD), ^{99}mTc -pyrophosphate (PYP), and ^{99}mTc -hydroxymethylene diphosphonate (HDP), termed “bone avid” and traditionally used for bone scintigraphy, have been shown to have high diagnostic accuracy for the identification of patients with ATTR-CA when coupled with an assessment for monoclonal proteins to exclude the substrate for AL amyloidosis. In the event that PYP is unavailable due to supply shortage, the investigator has the option of using HDP until PYP becomes available again to ensure study continuation per FDA.

